### **7.3 Concomitant Treatments**

Any medication used during the study should be recorded. The start and stop dates, total dose, route of administration, and indication for all concomitant medications should be recorded.

### **7.4 Treatment Compliance**

Compliance with the investigational product use will be documented.

## 8 ADVERSE EVENTS

### 8.1 Definition of an Adverse Event

An adverse event (AE) is defined as any undesired medical occurrence in a patient or clinical investigation patient receiving a pharmaceutical product which does not necessarily have a causal relationship with this treatment. An AE can therefore be any unfavorable sign and unintended sign (including an abnormal laboratory finding), symptom, or disease temporarily associated with the use of a study drug, whether or not related to the study drug.

Assessment of severity of an AE will be rated according to the following categories:

Grade 1 (MILD): The symptom is barely noticeable to the study patient and does not influence performance or functioning. Concomitant medication is not ordinarily indicated for relief of mild Aes.
Grade 2 (MODERATE): The symptom is of sufficient severity to make the study patient uncomfortable and to influence performance of daily activities. Concomitant medication may be indicated for relief of moderate Aes.
Grade 3 (SEVERE): The symptom causes severe discomfort, sometimes of such severity that the study patient cannot continue in the study. Daily activities are significantly impaired or prevented by the symptom. Concomitant medication may be indicated for relief of severe Aes.

Determination of the relationship between the AE and the study drug will be made using the following guidelines:

Unrelated	The adverse event is unlikely to have been caused by study drug.
Possibly related	It is unclear whether the adverse event may have been caused by the study drug.
Related	The adverse event is likely to have been caused by study drug.

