## 1.2 Schedule of Assessments (SoA)

Visits will be conducted as described:

	Screen	Treatment					Hospitalization	Follow-up	
		1 	2	3	4	5		28	60
Study Day	-3 to Baseline						Every day until discharge		
Visit Window (± days)	--	--	--	--	--	--	--	3	3
COVID-19 diagnosis	X								
Informed consent	X								
Medical history and pre-existing conditions	X								
Inclusion/exclusion criteria	X	X							
Urine pregnancy test		X							
Demographics		X							
Randomization		X							
Treatment (active or placebo)		X	X	X	X	X			
Vital signs		X	X	X	X	X	X		
Blood oxygen saturation		X	X	X	X	X	X		
ECG (telemetry) 		X	X	X	X	X	X 		
Hematology 		X		X		X	X 		
Biochemistry 		X		X		X	X 		
Cytokine/chemokine assay 		X				X	X 		
Mortality							X	X	X
Ordinal scale for clinical status		X	X	X	X	X	X	X	X
NEWS2 score		X	X	X	X	X	X	X	X
Hospital LOS and ICU LOS		X	X	X	X	X	X	X	X
Date of intubation/extubation, days on ventilation			X	X	X	X	X	X	X
Concomitant medications		X	X	X	X	X	X	X	X
Adverse events		X	X	X	X	X	X	X	X

 Day 1 baseline assessments occur before the first dose of treatment; pregnancy test to be conducted as applicable.

 Telemetry or 12 ECG lead monitored once daily.

 Hematology and biochemistry tests are performed at baseline and every other day through hospitalization.

 Cytokine and chemokine assays are collected at baseline before treatment, at Day 5 after treatment, and at discharge.

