## 2.3 Previous Human Experience

Human serum albumin (HSA, 5%) is a human blood product approved by FDA for intravenous (IV) infusion to treat hypovolemia and other serious conditions, including ARDS (Polito 2013). Albumin and large molecules are removed to manufacture Ampion, the low molecular weight (< 5 kDa) ultrafiltrate of 5% HSA.

Ampion has been administered via inhalation to humans with severe COVID-19 in a Phase I clinical trial utilizing inhaled Ampion in treating respiratory distress in patients as a result of COVID-19 (AP-014). The results from this study to date (n=27 subjects) indicate inhaled Ampion may be safe and well-tolerated with no differences in the incidence, frequency, and severity of adverse events for patients treated with Ampion compared to control. Preliminary results from the AP-014 Phase I trial of inhaled Ampion indicate:

- **Ampion demonstrated an improvement in all-cause mortality in COVID-19 patients compared to standard of care (SOC).** A lower all-cause mortality rate of 8% is observed for the Ampion treatment group, compared to 21% in standard of care alone.
- **Patients who received Ampion required less hospitalization time.** The average hospital length of stay was 7 days for the Ampion group compared to 11 days for standard of care patients.
- **Patients who received Ampion required less oxygen** than standard of care alone, and 86% of Ampion patients were stable or had improvement compared to 75% of SOC patients.
- **More patients who received Ampion were stable or had improvement** on a scale of clinical improvement compared to standard of care alone. By day 5, 86% of patients who received Ampion were stable or had improvement compared to 75% of standard of care patients. This trend in improvement with Ampion treatment is noted as early as day 2 and continues to day 5.
- **Adverse events were the same between Ampion and standard of care,** and no drug-related serious adverse events have been reported.

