#### **5.1.5 Post-Treatment Follow-Up (Days 28, 60)**

The following procedures will be performed at all follow-up visits (Days 28, 60):

- Mortality
- Concomitant medications/therapies
- Hospital LOS
- ICU LOS
- Ordinal scale and NEWS2 assessments
- Aes

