### Serum Biochemistry

Biochemistry lab tests will be collected from the medical records at baseline and every other day through treatment and hospital stay (as applicable). In the case of a clinically significant abnormal lab result, continue to collect and test those samples to follow subject to resolution and/or discharge, whichever should occur first.

The following biochemistry lab tests are tested: sodium, potassium, chloride, bicarbonate, urea, creatinine, glucose, total calcium, phosphate, ferritin, high-sensitivity C-reactive protein (hs-CRP), protein, albumin, globulins, total bilirubin, alkaline phosphatase (ALP), alanine aminotransferase (ALT), aspartate aminotransferase (AST) and lactate dehydrogenase (LDH).

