### **8.3 Recording of Adverse Events and Serious Adverse Events**

Recording and reporting of adverse events should be in accordance with the FDA's final "Guidance for Industry and Investigators Safety Reporting Requirements for INDs and BA/BE Studies" of December 2012.

Any AE is to be recorded in the eCRF. In order to avoid vague, ambiguous, or colloquial expressions, the AE should be recorded in standard medical terminology rather than the patient's own words. Whenever possible, the investigator should combine signs and symptoms that constitute a single diagnosis.

The existence of an AE may be concluded from a spontaneous report of the patient; from the physical examination; or from special tests e.g., laboratory assessments, where applicable, or other study-specified tests (source of AE).

The reporting period begins from the time that the patient is randomized through index hospitalization until discharge or death, whichever should occur first. Any events continuing at study exit will be followed for 30 days or to resolution, or until no improvement is expected, whichever comes first. Any SAE occurring after the reporting period must be promptly reported if a causal relationship to the investigational drug is suspected. If the patient begins a new therapy, the safety reporting period ends at the time the new treatment is started, however, death must always be reported when it occurs during the study period irrespective of intervening treatment.

Each AE is to be evaluated for duration, severity, seriousness, and causal relationship to the investigational drug. The action taken and the outcome must also be recorded.

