4.1 Safety

Safety is measured by the incidence of adverse events (AEs) and serious adverse events (SAEs) from baseline to Day 60.

The hypotheses to be tested are:

$$H_0: \pi_A = \pi_S \text{ versus } H_A: \pi_A \neq \pi_S$$

Where π_A and π_S represent the proportion of patients who experience an AE or SAE for Ampion and Placebo during the first 60 days after randomization. The difference between Ampion and Placebo will be tested via an appropriate chi-square test or Fisher's exact test utilizing PROC FREQ with the EXACT option, if needed.

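### The Day 60 comparison of adverse event incidence ignores that events are looked for more closely in hospital, so it tends to favour the arm discharged sooner if stays differ and post-discharge capture is incomplete

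*Protocol*

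**What the plan says.** Protocol 8.1 defines AEs broadly: "An AE can therefore be any unfavorable sign and unintended sign (including an abnormal laboratory finding". Protocol 8.3 lists as sources a patient's spontaneous report and findings "from the physical examination; or from special tests e.g., laboratory assessments, where applicable, or other study-specified tests (source of AE".

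In hospital, the Schedule of Assessments (Protocol 1.2) marks AE review on each of Days 1 to 5 and then "Every day until discharge". On laboratory work it says: "Hematology and biochemistry tests are performed at baseline and every other day through hospitalization". Protocol 5.2 repeats this for biochemistry: "Biochemistry lab tests will be collected from the medical records at baseline and every other day through treatment and hospital stay (as applicable".

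After discharge, Protocol 5.1.5 opens its list with "The following procedures will be performed at all follow-up visits (Days 28, 60". The list includes AEs but no laboratory tests and no separate vital signs item. Protocol 3.1 says contact after treatment is typically by telephone unless the patient is still an inpatient.

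SAP 4.1 then tests the proportion of patients with an AE or SAE "during the first 60 days after randomization", by chi-square or Fisher's exact test. This endpoint stands first in the hierarchical order of secondary endpoints (Protocol 9.4.2, SAP 4).

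Two pairs of statements conflict:

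- Protocol 8.3 ends the AE reporting period at discharge or death, apart from deaths and later SAEs suspected to be drug-related. Protocol 9.3.1.4 and SAP 9.5 collect AEs to Day 60.
- SAP 4.1 tests AE incidence. SAP 4.8 says AE and SAE rates will be tabulated and not otherwise analysed.

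**The concern.** The chance that an AE is recorded depends on whether the patient is still in hospital, and time in hospital may itself depend on treatment. Hospital length of stay is a secondary efficacy endpoint, and Protocol 2.3 reports from Phase I: "The average hospital length of stay was 7 days for the Ampion group compared to 11 days for standard of care patients". A drug that shortens stay would also shorten the period of close observation, and a lower recorded AE count could follow from that alone. If Ampion lengthened stay, the distortion would run the other way.

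Nothing in SAP 4.1 separates the two effects. No common observation window, rate per day under observation, or split of in-hospital from post-discharge events is planned. What is at stake is mainly the safety conclusion. Because this is the first secondary test, a spurious significant result would also let testing move on to the next endpoint.

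**Working it through.** **Is there a plan figure to reproduce?** No. The documents give no AE incidence, AE detection rate or power for this endpoint. The stated power of at least 80% concerns Day 28 mortality and does not bear on this point.

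**Scheduled observation at the Phase I stays.** Count the stay from randomization.

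- AE contacts: 7 + 2 = 9 for Ampion, 11 + 2 = 13 for control.
- Laboratory days, every other day from Day 1: 4 (Days 1, 3, 5, 7) v 6 (Days 1, 3, 5, 7, 9, 11).

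**Model.**

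- From the documents: stays L of 7 and 11 days (Protocol 2.3), 100 per arm (Protocol 4.1), two-sided alpha 0.047 (SAP 7.1), 60-day window (SAP 4.1).
- Assumed: the same true AE rate h per day in both arms (0.02, 0.05 or 0.10), constant over 60 days; every in-hospital AE recorded; a fraction f of later AEs recorded; everyone in an arm has the same stay.

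P(at least one recorded AE) = 1 − exp(−h × [L + f × (60 − L)])

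The bracket is the effective number of days observed:

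- f = 0: 7 v 11
- f = 0.2: 7 + 0.2 × 53 = 17.6 v 11 + 0.2 × 49 = 20.8
- f = 0.5: 7 + 0.5 × 53 = 33.5 v 11 + 0.5 × 49 = 35.5

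Example with h = 0.05 and f = 0: 1 − exp(−0.35) = 29.5% v 1 − exp(−0.55) = 42.3%.

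The last two columns give the exact probability of a significant difference in either direction, summed over the two binomial distributions. Gaps were taken before rounding.

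| f | h per day | Recorded, Ampion v control | Gap (points) | Chi-square | Fisher |
|---|---|---|---|---|---|
| 0 | 0.02 | 13.1% v 19.7% | 6.7 | 23.8% | 18.6% |
| 0 | 0.05 | 29.5% v 42.3% | 12.8 | 46.2% | 40.5% |
| 0 | 0.10 | 50.3% v 66.7% | 16.4 | 65.7% | 60.6% |
| 0.2 | 0.02 | 29.7% v 34.0% | 4.4 | 9.6% | 7.3% |
| 0.2 | 0.05 | 58.5% v 64.7% | 6.1 | 14.3% | 11.3% |
| 0.2 | 0.10 | 82.8% v 87.5% | 4.7 | 14.7% | 10.6% |
| 0.5 | 0.02 | 48.8% v 50.8% | 2.0 | 5.2% | 4.0% |
| 0.5 | 0.05 | 81.3% v 83.1% | 1.8 | 5.9% | 4.0% |
| 0.5 | 0.10 | 96.5% v 97.1% | 0.6 | 5.0% | 1.5% |

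The nominal rate is 4.7%. At f = 0 and f = 0.2 nearly all the false results favour the shorter-stay arm. With f = 1 the gap is zero.

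**Sensitivity to the model.**

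- *Varying stays and AE rates.* Let stays follow a gamma distribution with mean 7 or 11 and coefficient of variation 0.7, and let patients' AE rates vary by a gamma factor with variance 1. Then P = 1 − E[1 / (1 + h × effective days)]. At f = 0.2 the false-positive rate falls to about 5% to 6% by Fisher and 7% to 8% by chi-square. At f = 0 it is still about 13% to 25% by Fisher.
- *Early onset.* Let onset times be exponential with mean 3, 5 or 10 days, with 0.5, 1 or 2 expected events per patient. At f = 0 the chi-square rate falls to 6% to 33%. At f = 0.2 it is about 6% with a mean onset of 3 days, but up to 19% with a mean of 10 days. At f = 0.5 it is 5% to 9%.

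**The case against.** A reader might infer that the arm discharged sooner will show fewer AEs, or that post-discharge AEs go unrecorded. The documents support neither. AEs are on the Day 28 and Day 60 lists, so the schedule reduces ascertainment without ending it. The telephone capture rate, the AE rate and this trial's difference in stay are all unknown. At 50% capture the constant-rate model shows almost no excess.

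The model is also generous to the concern in four respects:

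- Fixed stays and a constant rate for 60 days after a 5-day treatment mostly enlarge the effect. Protocol 9.4.2 names Fisher's test for binary outcomes, which lowers it further.
- The 7 v 11 days are preliminary figures from 27 subjects. They run from hospital admission (Protocol 5.2), whereas AE reporting starts at randomization (Protocol 8.3), so observed time is shorter than the stay.
- Prolonged hospitalization is itself an SAE criterion (Protocol 8.2). Stay is partly a result of AEs, and a shorter-stay arm may truly have fewer of them.
- The 0% rows describe complete loss after discharge. That would suit AEs detectable only by laboratory test, but no test of such AEs alone is planned. SAP 4.1 counts any AE or SAE.

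All of this limits the size. It does not remove the mechanism. Nor is low capture far-fetched: a site that follows Protocol 8.3 as written would report few ordinary AEs after discharge.

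**Conclusion.** The point holds as a conditional bias of unknown size. If stays differ by arm and post-discharge capture is incomplete, the SAP 4.1 comparison tends to favour the arm discharged sooner, even with equal true AE rates.

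Under equal constant rates of 0.02 to 0.10 per day, fixed stays of 7 v 11 days, 100 per arm and alpha 0.047, the chance of a false significant difference (Fisher to chi-square) is:

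- about 19% to 66% at 0% capture;
- 7% to 15% at 20% capture;
- about nominal or below at 50% capture.

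Varying stays reduce these figures. So do AEs that cluster in the first few days. The documents do not support reading the upper figures as the expected error rate of this trial.

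The two conflicts, on the AE collection period and on whether AE incidence is tested at all, need no assumption. They stand whatever the capture rate.

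**What to change.** Keep AE/SAE incidence to Day 60 as the protocol endpoint, and add to SAP 4.1:

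1. A supportive between-arm comparison of AEs with onset from first dose through Day 5. State that surveillance in this window is near-equal and not identical, because some patients will be discharged earlier (Protocol 7.1 allows for this).
2. AE rates per in-hospital patient-day by arm, with days counted from randomization. These are descriptive, since time in hospital is itself a post-randomization outcome.
3. Separate tables of in-hospital and post-discharge AEs by arm.
4. A sentence saying that any claim of fewer AEs on one arm will rest on agreement between these results and the Day 60 comparison.

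Reconcile Protocol 8.3 with Protocol 9.3.1.4 and SAP 9.5 on the AE collection period, and SAP 4.1 with SAP 4.8 on whether AE incidence is tested.

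The additions use data already scheduled for collection and need no new visits. The cost is SAP wording, one extra comparison, the rate and split tables, a protocol clarification on the collection period, and a somewhat more cautious safety conclusion.

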### 8.2 Definition of a Serious Adverse Event

A Serious Adverse Event (SAE) is any untoward medical occurrence that occurs at any dose that:

- Results in death
- Is life-threatening (patient is at immediate risk of death from the event as it occurred)
- Requires prolongation of existing hospitalization
- Results in persistent or significant disability/incapacity
- Results in any congenital anomaly/birth defect

Important medical events that may not result in death, are not life-threatening, or do not require hospitalization may be considered SAEs when, based on appropriate medical judgment, they may jeopardize the patient and may require medical or surgical intervention to prevent one of the outcomes listed in this definition. Examples of such events include allergic bronchospasm requiring intensive treatment or blood dyscrasias or convulsions that do not result in in-patient hospitalization.

Hospitalizations for elective surgery or other medical procedures that are not related to a treatment-emergent AE are not considered SAEs.

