### **9.3.1.4 Safety Data:**

Safety data will be presented by treatment arm. Safety data will be evaluated by changes in vital sign measurements, laboratory assessments, and the frequency and severity of AEs. Concomitant medication will be recorded for safety. AEs will be collected from baseline to Day 60. The severity of AEs (mild, moderate, severe), relatedness (related, possibly related, unrelated) along with the duration, action taken, and outcome (e.g., study withdrawal) will also be recorded.

All data collected under this study protocol will be included in the assessment of patient safety. Missing or incomplete AE data will assume greatest relationship to study drug and/or severity.

Remaining safety data will be collected from enrollment through index hospitalization until hospital discharge (or in-hospital death). Safety data will be tabulated and presented overall and by treatment group for the safety analysis population.

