### 9.4.2 Secondary Endpoints

Secondary endpoints assess the effect of inhaled Ampion treatment compared to placebo on the clinical outcomes for participants with respiratory distress due to COVID-19. The secondary endpoints will be tested in a hierarchical manner in the order presented, and thus no adjustment to the alpha level is necessary:

Objective	Endpoint
Secondary	
Assess the effect of Ampion compared to placebo on safety	

Incidence of adverse events (AEs) and serious adverse events (SAEs) from baseline to Day 60.

Assess the effect of Ampion compared to placebo on clinical health	

Change in NEWS2 score from baseline through Day 5.

Change in NEWS2 score from baseline to hospital discharge.

Objective	Endpoint
Assess the effect of Ampion compared to placebo on hospital stay	
 
Hospital length of stay (LOS) from admission to discharge.
 

Assess the effect of Ampion compared to placebo on oxygen use	
 
Change from baseline in oxygen use, blood oxygen saturation, and oxygen flow rate from baseline through Day 5.
 

Assess the effect of Ampion compared to placebo on progression to respiratory failure	
 
Percentage of participants who progress to respiratory failure (i.e., need for mechanical ventilation, ECMO, non-invasive ventilation) by Day 28.
 

Assess the effect of Ampion compared to placebo on intensive care	
 
Percentage of participants who require Intensive Care Unit (ICU) admission by Day 28.
 
ICU-free days through Day 28.
 
ICU LOS from ICU admission to discharge.
 

Assess the effect of Ampion compared to placebo on all-cause mortality	
 
Percentage of participants with a successful outcome (life) or unsuccessful outcome (death) by Day 28.
 

The efficacy endpoints will be evaluated to estimate the treatment effect and use descriptive statistics including mean, standard deviation, percentages, minimum/maximum, and 95% confidence intervals. All endpoints will be tabulated and presented by treatment arm, cohort (moderate and severe), and timepoint. Where appropriate, data will be tabulated and presented cumulatively across cohorts and/or timepoints.

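### The SAE criteria cover only prolongation of an existing stay, although Protocol 8.2 elsewhere presumes that a new admission counts and SAE incidence runs to Day 60

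*Protocol*

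**What the plan says.** Protocol 8.2 defines an SAE by five criteria: death, immediate threat to life, "Requires prolongation of existing hospitalization", lasting disability, and congenital anomaly. SAP 5.2 repeats the same five. Neither list names a new inpatient admission.

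Two further sentences in Protocol 8.2 bear on this. The first lets important medical events be classed as serious by judgment, and describes them partly as events that "do not require hospitalization may be considered SAEs when, based on appropriate medical judgment". The second is an exclusion: "Hospitalizations for elective surgery or other medical procedures that are not related to a treatment-emergent AE are not considered SAEs". SAP 5.2 has neither sentence.

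The endpoint window is longer than the index stay. Protocol 9.4.2 lists as its first secondary endpoint "Incidence of adverse events (AEs) and serious adverse events (SAEs) from baseline to Day 60", and SAP 4.1 states its hypothesis for events "during the first 60 days after randomization". Protocol 9.3.1.4 says "AEs will be collected from baseline to Day 60", and the Schedule of Assessments places AE assessment at the Day 28 and Day 60 contacts.

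Protocol 8.3 sets a shorter period for reporting: "The reporting period begins from the time that the patient is randomized through index hospitalization until discharge or death, whichever should occur first". After that, prompt reporting of an SAE is required only if a causal link to the drug is suspected. Deaths during the study are always reported.

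**The concern.** The hospital criterion works while the participant is in the index stay, because a complication that keeps the participant in hospital longer is serious. Once the participant has gone home there is no stay to prolong. The same complication leading to a new admission then meets no hospital criterion, although the admission would ordinarily be taken as the sign that the event was serious.

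The rest of Protocol 8.2 points the other way. An exclusion for elective admissions has little purpose unless other admissions count, and the important-medical-event clause sets its events apart from those that need hospital care. Two sites could each defend a different classification of the same readmission.

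What is at stake is SAE incidence to Day 60 as a reported endpoint, the treatment-emergent SAE table (SAP 11.1.3.4), and the oversight steps keyed to SAE status: eCRF entry within 24 hours (Protocol 8.4.1), routine DSMB review of SAEs (Protocol 3.5), and immediate DSMB review of a drug-related SAE (Protocol 6.1).

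**Working it through.** The documents state no figure on this point, so there is none to reproduce. The check applies the two lists, as written, to typical cases.

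| Case | Protocol 8.2 | SAP 5.2 |
|---|---|---|
| Complication extends the index stay | SAE (prolongation) | SAE (prolongation) |
| Non-elective readmission; not fatal, life-threatening or disabling; new stay not prolonged | Meets no listed criterion; SAE only if judged an important medical event | Meets no criterion; no judgment clause |
| Readmission with a fatal, life-threatening or disabling event | SAE | SAE |
| Readmission during which an event lengthens the new stay | That event is an SAE | That event is an SAE |
| Elective readmission unrelated to a treatment-emergent AE | Excluded | Meets no criterion |

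The second row is the gap. In the protocol the outcome depends on a discretionary clause. In the SAP the literal outcome is non-serious.

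**Share of the window exposed to the gap.** Inputs: mean stays of 7 days (Ampion) and 11 days (standard of care) from Protocol 2.3, and a 60-day endpoint window. Assumption: hospital admission at about Day 1. The share after discharge is (60 − stay)/60.

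- Stay of 7 days: (60 − 7)/60 = 53/60 = 88%.
- Stay of 11 days: (60 − 11)/60 = 49/60 = 82%.

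Admission before Day 1 would raise both shares. They describe time at risk for a participant discharged alive, not a number of events.

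**Effect on the SAP 4.1 test.** SAP 4.1 defines one proportion per arm: patients with an AE or an SAE. SAP 5.2 defines an SAE as a kind of AE, so every SAE is already an AE. A readmission event moved from serious to non-serious stays in the numerator, provided that it is recorded at all. Only the separate SAE count changes.

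**Whether the bullet alone would repair the problem.** Suppose that it named inpatient hospitalization. The second row would become an SAE in both documents. But Protocol 8.3 would still end the reporting period at index discharge and, after that, require a non-fatal SAE to be reported only on suspicion of causality. An unrelated readmission on Day 15 would be an SAE by definition without a duty in 8.3 to report it, while Protocol 9.3.1.4 and the endpoint expect it. The bullet and the reporting period have to change together.

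**The case against.** The strongest reply is that misclassification is not certain. A site that reads all of Protocol 8.2 could reasonably conclude that non-elective admissions count, and other routes to seriousness remain open after discharge. Protocol 8.3 and 8.4.2 also tie recording and reporting to FDA guidance and regulation, whose content lies outside these documents. This stands in part. It makes the likely result inconsistent classification rather than uniform omission. It does not rescue the lists, which are the explicit rule in both documents, and the SAP list carries none of the sentences that point the other way.

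A reader might also infer more than the documents support:

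- **A count of missed SAEs.** Assume that 5% to 15% of survivors are readmitted, with 74 to 92 survivors per 100 (the plan's 26% and 8% mortality). This gives 0.05 × 74 = 3.7 to 0.15 × 92 = 13.8 readmissions per arm. The rate is an assumption. The result also counts every readmission, including elective ones and those that are serious by another route, so it is not a number of missed SAEs.
- **Bias between arms.** Earlier discharge on Ampion would leave that arm more time in which admissions do not count. The only support is a 4-day difference in stay from preliminary Phase I data on 27 subjects. With the same assumed 5% to 15% spread evenly over the post-discharge time, four days hold between 5 × 4/53 = 0.4 and 15 × 4/49 = 1.2 readmissions per 100 survivors. The documents do not establish a material bias.
- **Loss of expedited reporting.** Protocol 8.4.1 confines this to unexpected serious suspected reactions, so an unrelated readmission would not qualify in any case. The DSMB also sees other clinically important safety findings, not SAEs alone (Protocol 3.5).

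**Conclusion.** Wrong as written. Both documents give a hospital criterion that a new admission does not meet, Protocol 8.2 contradicts it by implication, and the SAE endpoint covers weeks in which most surviving participants are expected to be at home. Followed literally, the rule makes a post-discharge readmission serious only by another route. Day 60 SAE incidence and SAP table 11.1.3.4 can therefore be understated, or can mix classifications across sites.

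The size in events cannot be computed from the documents. The 82% to 88% of the window after discharge rests on the Phase I mean stays and admission at about Day 1, and indicates exposure only. The defect itself does not depend on those figures. The primary endpoint, alpha and sample size are untouched. The SAP 4.1 proportion is largely unaffected if it is the single composite that its wording describes and the events are recorded as AEs.

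**What to change.** 1. In Protocol 8.2 and SAP 5.2, change the third bullet to: *Requires inpatient hospitalization (other than the index COVID-19 hospitalization) or prolongation of existing hospitalization.*
2. Keep the exclusion for elective procedures in Protocol 8.2.
3. Reconcile the Protocol 8.3 reporting period, including its causality condition for later SAEs, with the Day 60 endpoint and AE collection.
4. State that non-elective readmissions identified at the existing Day 28 and Day 60 calls are recorded as SAEs. Recording every readmission would conflict with item 2.

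The cost is one bullet in each document, an amendment to Protocol 8.3, and a line of eCRF guidance. No visit is added. The downside is somewhat more SAE reports and a higher stated SAE rate.
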